10.3.2. Definition of SAE or Serious Suspected Adverse Reaction

An AE or suspected adverse reaction is considered “serious” if, in the view of either the PI (or designee) or Sponsor, it results in any of the following outcomes:

- Death
- A life-threatening AE ([Section 10.1.7](#))
- Inpatient hospitalization or prolongation of existing hospitalization
- A persistent or significant incapacity or substantial disruption of the ability to conduct normal life functions
- A congenital anomaly/birth defect in the offspring of a patient who received study drug

Important medical events that may not result in death, be life-threatening, or require hospitalization may be considered serious when, based upon appropriate medical judgment, they may jeopardize the patient or patient and may require medical or surgical intervention to prevent one of the outcomes listed in this definition. Examples of such medical events include allergic bronchospasm requiring intensive treatment in an emergency room or at home, blood dyscrasias, or convulsions that do not result in inpatient hospitalization, or the development of drug dependency or drug abuse.

10.3.2.1. SAE Definition Clarifications

- Death is an outcome of an AE, and not an AE in itself
- All deaths during study drug infusion or occurring up to the EOS/ET visit, regardless of cause or relationship, must be reported
- “Occurring at any dose” does not imply that the patient is actively receiving study drug at the time of the event

- “Life-threatening” means that the patient was at immediate risk of death from the event as it occurred. This does not include an event that might have led to death, had it occurred with greater severity.
- Complications that occur during hospitalizations are AEs. If an AE prolongs hospitalization, it is an SAE.
- “In-patient hospitalization” means the patient has been formally admitted to a hospital for medical reasons, for any length of time. This may or may not be overnight. It does not include presentation and care within an emergency department (although an emergency department visit may define a medically important event, which is also considered an SAE).
- The PI (or designee) should attempt to establish a diagnosis of the event based on signs, symptoms, and other clinical information. In such cases, the diagnosis should be documented as the AE or SAE, rather than as the individual signs or symptoms.

10.3.3. Recording and Follow Up of AE and/or SAE

10.3.3.1. AE and SAE Recording

AEs that occur after signing the ICF, but before the first dose of study drug, will be recorded to the eCRF as medical history, unless related to a study procedure.

Any SAE that occurs after signing the ICF, but before the first dose of study drug, will be recorded to the eCRF as an SAE. The PI (or designee) will assess all AEs and SAEs and will record the following information on the appropriate eCRF:

- Date of onset
- Date of resolution or stabilization
- Severity
- Relationship to study drug
- Action taken with study medication

Events that, in the opinion of the PI (or designee), may represent intolerance of the IV infusion of study drug must be recorded as AEs on the eCRF. In general, these events will be temporally related to study drug infusion.

Laboratory abnormalities should not be recorded as AEs or SAEs unless they are associated with clinical signs or symptoms, require medical intervention or lead to interruption of study drug infusion or discontinuation. If the laboratory abnormality is part of a clinical condition or syndrome, it should be recorded as the syndrome or diagnosis rather than as the individual laboratory abnormality. In addition, laboratory abnormalities or other abnormal test assessments (eg, ECGs) that are associated with signs or symptoms must be recorded as AEs or SAEs if they meet the definition of an AE (or SAE) as described in [Section 10.3.1](#) (or [Section 10.3.2](#)).

Additional details can be found in the applicable study plans.

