2.3. Benefit/Risk Assessment

2.3.1. Risk Assessment

As this is the second clinical trial of LASN01 in humans, a full risk profile has not yet been characterized. In the Phase 1/2a clinical study (LASN01-CL-1101), no safety concerns have emerged to date. Patients in Parts C and D in the study have completed enrollment and are ongoing without additional safety signals observed with ongoing safety monitoring. Nonclinical studies and data from humans with genetic defects in IL-11 production show defects in bone development ([Nieminen 2011](#); [Keupp 2013](#)). Short-term exposures in adult patients in the proposed study are not expected to cause any developmental defects. Inhibition of fibrogenesis can potentially affect normal wound healing ([Allanki 2021](#)). However, IL-11 is not known to affect normal fibrotic processes or normal wound healing. Recombinant IL-11 is an approved treatment that stimulates thrombopoiesis. However, IL-11 knockout animals do not display platelet defects, and LASN01 and IL-11 have shown no effect on platelet numbers or function in nonclinical toxicology studies ([Section 2.2.2.2.1](#)). Liver function tests will be followed closely for any clinically significant, adverse changes.

An additional internal Lassen Therapeutics study investigated the ability of LASN01 to induce cytokine release in vitro using either peripheral blood mononuclear cells or whole blood. Results show that LASN01 has a low probability of inducing cytokine release in patients. In the subsequent healthy volunteer Phase 1 trial, no symptoms of cytokine release were observed in any of the patient cohorts, including the high dose of 1200 mg.

Data is pending on the effects of LASN01 withdrawal on the levels of IL-11 in circulation.

To ensure the safety of all patients, safety data will be closely followed for all patients.

No reproductive toxicity studies have been performed with LASN01. Based on published literature, reproductive development toxicity has been observed in IL-11 knockout mice. In contrast, humans with genetic mutations resulting in impaired IL-11R function appear fertile, despite displaying developmental effects such as a craniosynostosis-like phenotype ([Keupp 2013](#)). These data suggest fertility effects may be species specific.

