9.2.5. Safety Analyses

Safety will be assessed in the Safety Analysis Population.

Safety will be evaluated by presenting listings and summaries of AEs, vital signs, 12-lead ECGs, ophthalmic assessments, conventional clinical laboratory evaluations (serum chemistry, hematology, coagulation, and UA evaluations), prior and concomitant medication use, treatment compliance, and exposure. Safety variables will be tabulated by treatment arm, LASN01 dose level and placebo. Other safety measures (eg, physical examination findings, pregnancy test results, drug screening test results) will be listed.

AEs will be coded using the MedDRA version 24.1 or higher. The incidences of TEAEs will be presented by system organ class and preferred term according to MedDRA, by relationship to the study drug, by severity, and by whether or not they resulted in alteration of administration of or discontinuation of study drug. A TEAE is defined as an AE that occurs during or after the first study drug infusion. A TRAE is defined as an AE with a plausible temporal relationship between the onset of the AE and administration of study drug (and as further defined in [Table 6](#)). TEAEs will be captured until Day 365/Week 53. From this visit to the EOS visit, only TRAEs will be recorded. In addition, the incidences of serious TEAEs and TEAEs leading to discontinuation of study drug will be presented by system organ class, preferred term, and relationship to study drug.

Descriptive statistics and change from Baseline for clinical laboratory test and vital sign results will be presented by scheduled time point. Incidences of potentially clinically significant clinical laboratory results, determined based on normal ranges, will also be summarized by scheduled time point. The numbers and percentages of abnormal 12-lead ECGs will be provided by scheduled time point.

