10.3.1. Definition of AE

An AE means any untoward medical occurrence associated with the use of a drug in humans, whether or not considered study drug related. An AE (also referred to as an adverse experience) can be any unfavorable and unintended sign (eg, an abnormal laboratory finding), symptom, or disease temporally associated with the use of a drug and does not imply any judgment about causality. An AE can arise with any use of the study drug (eg, off-label use, use in combination with another drug) and with any route of administration, formulation, or dose, including an overdose. The following are not AEs:

- Any non-serious AE that occurs after signing the ICF, but before dosing, unless related to a study procedure
- Any clinically significant abnormal laboratory findings or other abnormal safety assessments that are associated with the underlying disease, unless judged by the PI (or designee) to be more severe than expected for the patient's condition
- The disease/disorder being studied or expected progression, signs, or symptoms of the disease/disorder being studied, unless more severe than expected for the patient's condition)
- Medical or surgical procedure (eg, endoscopy, appendectomy): the condition that leads to the procedure is the AE
- Situations in which an untoward medical occurrence did not occur (eg, social and/or convenience admission to a hospital)
- Anticipated day-to-day fluctuations of pre-existing disease(s) or condition(s) present or detected at the start of the study that do not worsen
- Clinical changes consistent with progression of the underlying disease (ie, TED).

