10.3.3.2. Assessment of Intensity

All AEs will be graded for severity ([Table 5](#)).

The PI (or designee) will use the terms: Mild, Moderate, or Severe to describe the maximum intensity of the AE. For purposes of consistency, these intensity grades are defined in [Table 5](#).

Table 5. Guidelines for Severity Assessments

CTCAE Criteria	Category	Description
1	Mild	Asymptomatic or mild symptoms; clinical or diagnostic observations only; intervention not indicated
2	Moderate	Minimal, local, or noninvasive intervention indicated; limiting age-appropriate instrumental activities of daily living
3	Severe	Medically significant but not immediately life-threatening; hospitalization or prolongation of hospitalization indicated; disabling; limiting self-care activities of daily living
4	Life-threatening	Life-threatening consequences; urgent intervention indicated.
5	Death	Death related to AE

CTCAE = Common Terminology Criteria for Adverse Events
Source = [CTCAE V5 2017](#)

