12.11 Electrocardiogram

Electrocardiograms (ECGs) will be measured in triplicate within a 15-minute period, separated by 1 minute or more. Heart rate (HR), and the PR, RR, QRS, QT, and QTcF (QT interval corrected using Fridericia's formula) intervals will be summarized using continuous descriptive statistics by treatment arm and for all patients at each planned data collection visit and time point. Change from baseline to each post-baseline visit and time point will be also summarized by treatment arm.

A patient listing of the ECG results will be produced. The results for ECG will also be graded as normal, abnormal NCS, or abnormal CS, and these ECG results will be listed only.

CONFIDENTIAL

The contents of this document are confidential to [REDACTED]
Unauthorized use, disclosure, or reproduction is strictly prohibited.

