12.12 Clinical Laboratory Data

Clinical laboratory data including hematology, coagulation, serum chemistry, urinalysis, urine drug screen, and additional tests (Follicle-stimulating hormone as applicable, Hepatitis B virus surface antigen, Hepatitis C virus antibody, Human immunodeficiency virus antibody [HIV-1 and HIV-2], severe acute respiratory syndrome coronavirus 2 by polymerase chain reaction (PCR) antibody test, serum or urine pregnancy [for females of childbearing potential only]) are collected at each planned data collection visits.

The quantitative variables will be summarized by treatment arm with continuous descriptive statistics. Change from baseline will also be summarized by treatment arm and for all patients. Categorical results will not be summarized. Listings will be produced including an additional listing for abnormal values only.

13. Pharmacokinetic Analyses

PK will be assessed using the PK Population. placebo patients will not be assessed for PK. Where the data allow, noncompartmental analyses (NCA) will be used to estimate Day 1 serum PK parameters for LASN01 after single and repeat IV dosing. Final analyses will be performed after the database lock and will use actual sampling times. The effect of antidrug antibodies (ADA) on LASN01 exposure will be assessed. A PK report will be generated summarizing the results.

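### The SAP drops the protocol's incidence tables for abnormal laboratory results and ECGs without saying so, leaving silent liver-test changes in no specified by-arm count

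*Protocol*

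**What the plan says.** **Planned tables.** Protocol Section 9.2.5 states: "Incidences of potentially clinically significant clinical laboratory results, determined based on normal ranges, will also be summarized by scheduled time point". The same paragraph plans numbers and percentages of abnormal 12-lead ECGs by scheduled time point.

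**SAP tables.** SAP Section 1 gives the SAP's statistical methods precedence over the protocol's. Section 12.12 summarizes quantitative laboratory variables and their change from baseline with continuous statistics, then says "Categorical results will not be summarized" and provides listings, one of them restricted to abnormal values. Section 12.11 summarizes ECG intervals as continuous data. Of the normal / abnormal NCS / abnormal CS grades it says "these ECG results will be listed only".

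**AE recording.** Protocol Section 10.3.3.1 says "Laboratory abnormalities should not be recorded as AEs or SAEs unless they are associated with clinical signs or symptoms, require medical intervention", and the sentence goes on to exempt abnormalities that interrupt or end dosing. Section 10.3.1 says an AE "can be any unfavorable and unintended sign (eg, an abnormal laboratory finding), symptom". Grade 1 in Table 5 (Section 10.3.3.2) is described as "Asymptomatic or mild symptoms; clinical or diagnostic observations only; intervention not indicated".

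**Stated interest in liver tests.** Protocol Section 2.3.1: "Liver function tests will be followed closely for any clinically significant, adverse changes".

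**The concern.** Changes from baseline in laboratory values and ECGs, compared with placebo, are primary safety endpoints in both documents. Under Section 10.3.3.1, a laboratory abnormality can be clinically significant in the investigator's view and still not be an AE, provided it causes no symptoms, needs no intervention and does not interrupt or end dosing. The incidence table in Section 9.2.5 was the planned place where such patients would be counted by arm. Once the SAP removes it, the two gaps fall on the same patients. The comparison with placebo then rests on means, extremes and a reader's own count from a listing. Because Section 16 is silent, a reader of the study report would not learn that a planned safety summary had been withdrawn.

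**Working it through.** No figure in the plan bears on this point, so the check is a comparison of sections, followed by small illustrations on assumed values.

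**1. Protocol against SAP.**

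| Item | Protocol 9.2.5 | SAP | Reported in SAP 16? |
|---|---|---|---|
| Laboratory | Continuous summaries plus incidence of potentially clinically significant results by time point | 12.12: continuous summaries, listings | No |
| ECG | Number and percentage abnormal by time point | 12.11: intervals as continuous data; grades listed | No |
| Physical examination | Listed | 12.8: counts and percentages of normal / NCS / CS | No |

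The SAP also tabulates normal / NCS / CS for visual fields (12.3), slit lamp (12.5) and fundoscopy (12.7). It therefore does more than the protocol asked for physical examination and less for laboratory results and ECGs.

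**2. Does early termination explain it?** Section 16 restricts tables to Hertel proptosis and Total CAS and moves the other secondary and exploratory endpoints to listings. Laboratory and ECG changes are primary safety endpoints (protocol Section 3, SAP Section 2), and SAP Section 12 keeps the other safety tables. The bullet does not reach them.

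**3. Where a silent abnormality appears.** Take a patient with a raised transaminase, no symptoms, no intervention and uninterrupted dosing.
- TEAE tables (SAP 12.1): no, because no AE is recorded.
- Laboratory incidence table: none is specified.
- Continuous summaries: the value contributes to the mean and extremes.
- Abnormal-value listing: yes.
- Protocol 8.2.8: clinically significant abnormalities are followed, and diagnosis and resolution date go to the eCRF. No SAP section in the text reviewed says how these are summarized.

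Assume 3 such patients among 8 + 8 = 16 on LASN01 and 0 among 8 on placebo. True incidence is 3/16 = 18.75% against 0/8 = 0%. The specified incidence tables count 0 and 0.

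**4. Why by-visit statistics do not substitute.** Assume one arm of 8, all at 0.6 × ULN at baseline, and an abnormal reading of 5 × ULN (both multiples are assumptions). In scenario A the same patient is abnormal at three visits. In scenario B three different patients are abnormal, one at each visit. At each visit, in both scenarios:
- mean = (5 + 7 × 0.6)/8 = 9.2/8 = 1.15
- mean change = 1.15 − 0.60 = 0.55
- median 0.6, maximum 5

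Every by-visit statistic is the same, yet 1/8 patients are affected in A and 3/8 in B. A by-visit incidence table also shows 1/8 at each visit in both. Restoring the Section 9.2.5 table is therefore necessary but not sufficient. Only a row counting patients with any such post-baseline value separates the two.

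**5. Effect on the suspension rule.** The first criterion in protocol Section 7.4 needs a related SAE or severe AE of similar origin in at least 3 patients. Let p be an assumed rate of related severe laboratory abnormality among 16 LASN01 patients and q the share recorded as AEs. Then P(X ≥ 3) with X ~ Binomial(16, pq) is:

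| p | q = 1 | q = 0.5 | q = 0 |
|---|---|---|---|
| 0.10 | 21% | 4% | 0% |
| 0.20 | 65% | 21% | 0% |
| 0.30 | 90% | 44% | 0% |

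Under these assumptions non-recording lowers the chance of reaching that one criterion. It removes it only if no case meets any recording condition.

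**The case against.** A reader might infer that silent laboratory abnormalities can never be AEs and so cannot trigger the suspension rule. The documents do not support this.
- Abnormalities that "require medical intervention or lead to interruption of study drug infusion or discontinuation" are recorded without any symptom, and one that is part of a diagnosis is recorded as that diagnosis.
- Section 7.4 suspends enrollment on any of its criteria. One is the identification of unacceptable risk, which needs no AE record.
- Section 10.3.2 gives blood dyscrasias as an example of an event that may be serious.
- An asymptomatic rise with no intervention could well be graded mild under Table 5. It would then not count toward the 3-patient criterion even if it were recorded.
- The final SAP tables do not feed Section 7.4.

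It is also tempting to call platelets a named risk. Section 2.3.1 raises them because recombinant IL-11 stimulates thrombopoiesis, then reports no effect on number or function in nonclinical toxicology studies. Section 8.3.5 identifies no AESIs.

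Nor do Sections 10.3.1 and 10.3.3.1 flatly contradict each other. The first says what an AE can be, the second says what is recorded, and Table 5 grades events already classed as AEs. The wording still leaves room for sites to differ.

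Two points count against the tables themselves. With about 24 randomized patients, the abnormal-value listing lets a careful reader count patients and see repeats. The sentence on categorical results in SAP 12.12 may also mean only qualitative tests such as serology. Both are fair. But a listing is not a by-arm comparison, and on the narrower reading Section 12.12 still specifies no abnormality table.

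**Conclusion.** The point holds as a reporting gap. Two summaries planned in protocol Section 9.2.5, laboratory incidence and ECG abnormality counts, are absent from the SAP sections that should contain them, and Section 16 discloses neither. Laboratory abnormalities that meet no condition in Section 10.3.3.1, liver tests included, then appear in no specified by-arm incidence table. In the assumed case a difference of 3/16 against 0/8 would be tabulated as 0 against 0.

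The conclusion does not extend to patient safety oversight: the values remain listed, clinically significant results are followed, and the suspension rule is not disabled. It rests on the SAP text through Section 17. Section 18 (the list of tables) was not in the text reviewed, so a table named only there cannot be excluded. The rates and ULN multiples used above are illustrations and do not come from the documents. The change is worth making before reporting, because it concerns a primary safety comparison.

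**What to change.** 1. **SAP 12.12:** restore the Section 9.2.5 laboratory table by arm and visit. Add an any-post-baseline (worst value) row giving the number and percentage of patients per arm, at least for ALT, AST, GGT, total bilirubin and platelets. State the thresholds for potentially clinically significant values before database lock; the protocol says only that they are based on normal ranges.
2. **SAP 12.11:** restore counts and percentages of normal / abnormal NCS / abnormal CS ECGs by arm and visit, in the format of 12.3, 12.5, 12.7 and 12.8.
3. **SAP 16:** list and justify any departure from Section 9.2.5 that remains.
4. **Protocol 10.3.1, 10.3.3.1 and Table 5:** reconcile these on whether a clinically significant asymptomatic laboratory finding is an AE. With the study terminating early this has little effect on data already recorded, so the SAP tables come first.

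The cost is two more tables from data already collected.

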10.3.3.2. Assessment of Intensity

All AEs will be graded for severity ([Table 5](#)).

The PI (or designee) will use the terms: Mild, Moderate, or Severe to describe the maximum intensity of the AE. For purposes of consistency, these intensity grades are defined in [Table 5](#).

Table 5. Guidelines for Severity Assessments

CTCAE Criteria	Category	Description
1	Mild	Asymptomatic or mild symptoms; clinical or diagnostic observations only; intervention not indicated
2	Moderate	Minimal, local, or noninvasive intervention indicated; limiting age-appropriate instrumental activities of daily living
3	Severe	Medically significant but not immediately life-threatening; hospitalization or prolongation of hospitalization indicated; disabling; limiting self-care activities of daily living
4	Life-threatening	Life-threatening consequences; urgent intervention indicated.
5	Death	Death related to AE

CTCAE = Common Terminology Criteria for Adverse Events
Source = [CTCAE V5 2017](#)

10.3.3.3. Assessment of Causality

PI (or designee) should use their knowledge of the patient, the circumstances surrounding the event, and an evaluation of any potential alternative causes to determine whether an AE is considered to be related to the study drug, indicating "yes" or "no" accordingly.

The following guidance should be taken into consideration (see also [Table 6](#)):

- Temporal relationship of event onset to the initiation of study drug
- Course of the event, with special consideration of the effects of dose reduction, discontinuation of study drug, or reintroduction of study drug (as applicable)
- Known association of the event with the study drug or with similar treatments
- Known association of the event with the disease under study
- Presence of risk factors in the patient or use of concomitant medications known to increase the occurrence of the event
- Presence of non-treatment-related factors that are known to be associated with the occurrence of the event

These criteria, in addition to good clinical judgment, should be used as a guide for determining the causal assessment. If the event is believed to be not related or unlikely related to study drug infusion, then an alternative explanation should be provided.

Table 6. Guidelines for Assessing Relationship of Event to Study Drug

Is the adverse event suspected to be caused by the study drug on the basis of facts, evidence, science-based rationales, and clinical judgment?	
Related	There is a plausible temporal relationship between the onset of the adverse event and administration of study drug, and the adverse event cannot be readily explained by the patient's clinical state, intercurrent illness, or concomitant therapies; and/or the adverse event follows a known pattern of response to the study drug; and/or the adverse event abates or resolves upon discontinuation of the study drug or dose reduction and, if applicable, reappears upon rechallenge. An adverse event will be considered "Related", unless it fulfills the criteria specified for "Not Related".
Not Related	Evidence exists that the adverse event has an etiology other than the study drug (eg, preexisting medical condition, underlying disease, intercurrent illness, or concomitant medication); and/or the adverse event has no plausible temporal relationship to administration of the study drug (eg, cancer diagnosed 2 days after first dose of study drug).

